	
To our knowledge, the pharmacokinetics of relebactam, with or without imipenem, have not been studied in critically ill patients with ARC. If ARC affects relebactam clearance to a similar degree as imipenem and other renally eliminated β-lactams, larger doses or prolonged infusion may be required to maintain optimized pharmacodynamic exposure. Importantly, the effect of ARC on beta-lactam exposure is highly dependent on the MIC of the causative organism. Therefore, it is also possible that the lower MICs observed with imipenem when combined with relebactam may mean that ARC has little effect on achievable time above the MIC exposure.

2.3 Study Design
	
This will be a single center, observational, pharmacokinetic study. Eligible patients will be evaluated for inclusion/exclusion criteria. Following consent by the patient, legal authorized representative (LAR), or next of kin, participants will receive a single dose of imipenem-cilastatin-relebactam 1.25 grams administered as a 30 minute infusion. Blood samples will be collected over the following 6 hours (consistent with proposed dosing interval) for characterization of imipenem and relebactam concentrations. Pharmacokinetic analyses will be conducted to describe parameter estimates in patients with ARC. We aim to enroll up to 12 patients so that complete data for 8 patients with ARC can be collected.

2.4 Study Flowchart
	
N/A

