All participants will receive a single dose of imipenem-cilastatin-relebactam 1.25 grams as a 30 minute (+/- 5 minutes) infusion. Imipenem-cilastatin-relebactam vials will be supplied by the study sponsor. The dose will be prepared according to manufacturer recommendations in precisely 100 ml of 0.9% sodium chloride. Imipenem-cilastatin-relebactam must be administered through a peripheral intravenous catheter, peripherally inserted central catheter (PICC), central line, or port-a-catheter, whichever is determined to be most appropriate by the local investigator and care provider for each participant. Participants will also receive standard intravenous antibiotic therapy (excluding generic or branded intravenous imipenem) to treat their suspected infection, as determined by the responsible provider. No other intravenous medications will be co-administered with imipenem-cilastatin-relebactam.

Study Day 1

- Within 8 hours of beginning study medication infusion, a pre-dose SCr will be collected to confirm calculated CrCL remains ≥130 mL/min and that no change in SCr was observed to be ≥ 0.3 mg/dL from the baseline SCr used qualifying for enrollment.
- An 8 hour (± 1 hour) urine creatinine collection will be initiated within 4 hours prior to study medication infusion. The results of the measured urine CrCL will be used to confirm ARC in the patient over the time period that blood samples for imipenem-cilastatin-relebactam are collected.

$$\text{Measured CrCL (ml/min)} = \frac{\text{UCr (mg/dL)} \times \text{urine volume (mL)}}{\text{Predose-SCr} \times \text{time}^a}$$

Abbreviations: CrCl = creatinine clearance; SCr = serum creatinine; UCr = urine creatinine.

^a Time = The 8-hour urine collection has a ± 1 hour window (i.e., 480 min \pm 60 min); use the exact number of minutes of the urine collection in the equation

- Vital signs (temperature, heart rate, blood pressure, respiratory rate) will be recorded within 15 minutes prior to starting the study drug infusion.
- Participants will receive the single dose of imipenem-relebactam as described above. Exact start and stop times will be recorded in military time.
- Identify, assess, and record any new adverse events or Serious Adverse Events (SAE)
- Concomitant medications will be recorded.

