- Blood Sample Collection: Seven blood samples (4 ml per sample) will be collected in K2EDTA vacutainers at the following time points to determine the concentrations of imipenem and relebactam in plasma: 0 hour (within 30 minutes prior to the start of infusion), 0.5 hours (end of infusion), 0.75, 1, 2, 4, and 6 hours after the start of the infusion. The timing of all blood samples should be \pm 5 minutes of protocol defined time, except for the 0.5 hour (peak concentration), which can be + 5 minutes and should be collected as close to the end of the infusion as possible. All blood samples will be collected via a peripheral intravenous catheter inserted into the contralateral arm to drug administration for collection of blood samples. Alternatively, venipuncture may be used to collect the seven blood samples.
- Blood samples will be immediately stored on ice and centrifuged within 30 minutes of collection at 1000-1300 x g (rcf) for 10 minutes at 4°C to separate the plasma.
- Immediately after centrifugation of whole blood, use a 1.0 mL pipette to transfer exactly 1.0 mL of plasma to labeled, cryovials containing 1.0 mL of plasma stabilizer (2-(N-morpholino) ethanesulfonic acid (MES)). Add a second 1.0 mL of plasma to a second cryovial to serve as a back-up sample.
- Cap the cryovials and mix the plasma with the preservative stabilizer by inverting at least six times. Freeze and store at -80 °C. No more than 60 minutes should elapse between the blood draw and freezing of plasma sample.
- An additional 8ml blood sample will be collected for imipenem and relebactam protein binding determination at 0.5 hours (end of infusion). Plasma will be separated by centrifugation as previously explained. Approximately 0.9 mL of plasma will be loaded in an ultrafiltration device (Centrifree®, Merck Millipore Ltd., Ireland) and centrifuged for 45 minutes at 10° C at 2,000 x g to obtain an ultrafiltrate containing only free-drug concentrations. Protein binding will be conducted in triplicate. The protein-free ultrafiltrate volume will be measured, transferred to a cryovial and then, an equal volume of the stabilizer will be added (confirmation of processing instructions for protein-free imipenem and relebactam will be provided by Q2 Solutions, Ithaca, NY). The cryovials will be stored at -80° C until concentration determination. The final protein percentage will be calculated by dividing the free concentration by the total plasma concentration and subtracting from 100 (%).

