of best fit. Half-life ($T_{1/2}$) will be calculated as $\ln(2)/\lambda_z$. Area under the curve for the dosing interval ($AUC_{0-\tau}$) will be calculated by the linear/log trapezoidal rule (linear during increasing concentrations, log during decreasing concentrations), where τ is the dosing interval for the drug studied. The AUC to infinity (AUC_{INF}) will be calculated as the AUC extrapolated to infinity by the equation: $AUC + C_{last}/\lambda_z$. Clearance (CL) will be estimated by $Dose/AUC_{0-\tau}$. The volume of distribution based on the terminal elimination phase (V_z) will be estimated by $Dose/(\lambda_z * AUC_{0-\tau})$.

Population Pharmacokinetic Analyses

Imipenem and relebactam concentrations will be modeled using the non-parametric adaptive grid program (NPAG) with adaptive gamma in the Pmetrics package for R (Laboratory of Applied Pharmacokinetics and Bioinformatics, Los Angeles, CA) using either a one or two compartment model. Appropriate model selection will be based on visual inspection, observed versus predicted plots, and Akaike Information Criterion (AIC). The effect of specific body size descriptors (actual body weight, ideal body weight, body mass index, body surface area) and both calculated and measured CrCL will be analyzed for correlation with pharmacokinetic parameters (i.e., CL and volume of distribution).

Monte Carlo Simulation

Using the population pharmacokinetic model, a 5000 patient Monte Carlo simulation will be conducted for the standard imipenem and relebactam dosing regimen to determine probability of achieving pharmacodynamic thresholds, as defined by Sponsor, at the imipenem susceptibility breakpoint of 2 µg/mL. Observed fraction unbound estimates from the protein-free ultrafiltrate studies in these patients will be incorporated into simulations. In the scenario that the probability of target attainment (PTA) is less than 90%, a higher dose and longer infusion time (e.g., 2-3 hours) will be simulated to determine a dose that achieves at least 90% PTA. Analyses will also be conducted using contemporary MIC distributions of *P. aeruginosa* and KPC producing *K. pneumoniae*.

Power/Sample Size:

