Based upon relebactam single dose pharmacokinetic data from healthy volunteers receiving the drug with or without imipenem (3), clearance across all doses was 8.6 L/h with a standard deviation of 1.2 L/h. Eight in the ARC group would provide 80% power at an alpha of 0.05 to detect a 40% difference in total body clearance from the historical healthy volunteer data; this also assumes an increase in coefficient of variability (CV) to 25%, which is expected in critically ill patients. Since some patients with calculated CrCL via Cockcroft-Gault will not have 8 hour urine CrCL of at least 130 ml/min/1.73 m², this study will enroll up to 12 patients to have complete data for 8 patients with ARC. Enrollment will stop once complete data for 8 patients who meet the definition of ARC is confirmed or a maximum of 12 patients complete the study, whichever occurs first.

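### Non-compartmental CL and Vz divide a single dose by AUC0-τ, which leaves out the area after 6 hours and biases both parameters upward

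*Combined protocol and SAP*

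**What the plan says.** Section 2.3 describes a one-dose study: "participants will receive a single dose of imipenem-cilastatin-relebactam 1.25 grams administered as a 30 minute infusion". It ties the sampling window to the dosing interval: "Blood samples will be collected over the following 6 hours (consistent with proposed dosing interval". Section 2.5 sets the post-dose samples at "0.5 hours (end of infusion), 0.75, 1, 2, 4, and 6 hours after the start of the infusion", after a pre-dose sample. Imipenem within the previous 3 days is an exclusion.

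Section 2.7 (Non-compartmental) defines two areas. AUC0-τ is taken over the dosing interval by the linear/log trapezoidal rule. AUC_INF "will be calculated as the AUC extrapolated to infinity by the equation" AUC + Clast/λz. The next sentence reads "Clearance (CL) will be estimated by $Dose/AUC_{0", and the subscript continues to τ. Vz is then Dose/(λz × AUC0-τ). AUC_INF is used for neither parameter, and nothing in the document assumes steady state or corrects for the missing tail.

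The power paragraph of section 2.7 compares total body clearance with healthy-volunteer relebactam data, in which "clearance across all doses was 8.6 L/h with a standard deviation of 1.2 L/h".

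**The concern.** Over one dosing interval at steady state, the amount eliminated equals one dose, so Dose/AUC0-τ is clearance. After a first and only dose, some drug is still in the body at τ. The area to τ is then smaller than the total area, and dividing by it gives a clearance that is too high in expectation. Vz is inflated by the same factor.

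Objectives 1 and 2 are the single-dose pharmacokinetics of imipenem and relebactam, and section 2.7 plans these parameters for each of the 8 participants. The bias points towards the effect the study is looking for. At a given volume it grows as elimination slows, so it is largest when ARC has no effect on clearance, which is the null hypothesis of section 2.1.1.

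**Working it through.** **The plan's own figure.** Section 2.7 claims 80% power with n = 8, alpha 0.05, a 40% difference from 8.6 L/h and a CV of 25%. The difference is 0.40 × 8.6 = 3.44 L/h, the raised clearance is 12.04 L/h, and the SD is 0.25 × 12.04 = 3.01 L/h. A two-sided one-sample t-test has noncentrality 3.44/(3.01/√8) = 3.23 and power 79.1%, which reproduces the claim. An 8-versus-8 comparison pooling SDs of 1.2 and 3.01 gives 79.7%, so the arithmetic does not identify the test. None of these calculations includes the truncation bias.

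**Inputs for the bias.** From the documents: infusion time T = 0.5 h, τ = 6 h, and relebactam clearance of 8.6 L/h (no ARC effect) or 12.04 L/h (the design effect). Assumed, because the documents give neither volume nor half-life: one compartment and V = 15, 20 or 25 L.

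**Formula.** With k = CL/V, the fraction of the total area lying beyond 6 h is

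f = [(1 − exp(−kT))/(kT)] × exp(−k(6 − T)).

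Then Dose/AUC0-τ = CL/(1 − f), an overstatement of f/(1 − f). Vz has the same relative overstatement when λz is unchanged.

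**Example.** For CL 8.6 and V 20, k = 0.43 per hour and kT = 0.215. So f = (0.1935/0.215) × exp(−2.365) = 0.900 × 0.0939 = 8.45%, and the overstatement is 0.0845/0.9155 = 9.23%.

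| True CL (L/h) | V (L) | Half-life (h) | f | CL and Vz overstated by | Apparent CL against 8.6 |
|---|---|---|---|---|---|
| 8.6 | 15 | 1.21 | 3.71% | 3.9% | +3.9% |
| 8.6 | 20 | 1.61 | 8.45% | 9.2% | +9.2% |
| 8.6 | 25 | 2.01 | 13.85% | 16.1% | +16.1% |
| 12.04 | 15 | 0.86 | 1.00% | 1.0% | +41.4% |
| 12.04 | 20 | 1.15 | 3.15% | 3.3% | +44.6% |
| 12.04 | 25 | 1.44 | 6.29% | 6.7% | +49.4% |

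In terms of half-life alone, the bias is 1.9% at 1 h, 7.6% at 1.5 h and 15.8% at 2 h, and it reaches 10% at about 1.66 h.

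**On the plan's sampling times.** The linear-up/log-down rule was applied to error-free concentrations at 0, 0.5, 0.75, 1, 2, 4 and 6 h. Across the six cases, Dose/AUC0-τ is 2.1% to 16.4% too high and Dose/AUC_INF is 0.2% to 1.1% too high.

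**With measurement error.** Assumptions: 10% lognormal error on each concentration, λz from the last three samples, 20,000 profiles per case. The root-mean-square error of CL is 5.2% to 17.1% with AUC0-τ and 4.2% to 4.8% with AUC_INF. AUC_INF is better in all six cases.

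**Illustration only.** Suppose non-compartmental CL were tested against 8.6 L/h (two-sided one-sample t, n = 8, CV 25%), and the historical value had used the area to infinity. With no true difference, the type I error would be about 6.5%, 13% or 27% at V = 15, 20 or 25 L. The plan names no test and does not say how 8.6 L/h was derived.

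**The case against.** The strongest case on the other side concerns size and reach, since the formula itself is not in dispute.

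- **Size.** No volume or half-life is given, and if half-life is about 1 h or shorter the bias is 2% or less. At the design effect the bias is 1.0% to 6.7%, below the standard error of mean CL (25%/√8 = 8.8%; 95% half-width about 21%). This stands as a limit on magnitude. But a bias in a known direction is not excused by being smaller than the sampling error when the unbiased quantity is already calculated.
- **Individual estimates.** With 10% assay error at CL 12.04, Dose/AUC0-τ still falls below the true value in roughly 34%, 21% and 7% of simulated profiles (V = 15, 20, 25 L). The upward bias therefore describes the formula and not every single estimate. Likewise, that it is larger without an ARC effect holds only at a given volume.
- **Type I error.** Those figures need a test the plan does not name, and a historical value free of the same truncation. If the 8.6 L/h was truncated in a similar way, part or all of the bias would cancel. They should carry little weight, and the finding does not depend on them.
- **Reach.** "Using the population pharmacokinetic model, a 5000 patient Monte Carlo simulation will be conducted", so Objective 3 and the covariate work on CL within that model do not use AUC0-τ. This is correct and limits the severity.
- **Reliance on λz.** Using AUC_INF makes CL depend on λz, which section 2.7 describes only as the slope of a best-fit line, without a rule for choosing points. The precision check covers one compartment and no values below quantification. This is a reason to list the extrapolated percentage, not to drop the tail.

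**Conclusion.** The concern holds. For a single-dose study, the CL and Vz formulas in section 2.7 are wrong as written and are biased upward for both drugs. The direction does not depend on any assumption. The size does: for relebactam, with one compartment and V of 15 to 25 L, it is 3.9% to 16.1% at 8.6 L/h and 1.0% to 6.7% at 12.04 L/h. A true difference of zero would then be reported as about +4% to +16%, and a true +40% as about +41% to +49%. A slower second phase, which the plan's modelling section allows for, would increase the omitted area.

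The error affects the non-compartmental results for Objectives 1 and 2. It would affect the comparison with historical clearance only if the non-compartmental estimate is the one compared, which the power paragraph does not say. It should be fixed, but it does not threaten the dose-finding simulation.

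**What to change.** In section 2.7 (Non-compartmental), replace the two formulas with text such as: *CL will be estimated by Dose/AUC_INF and Vz by Dose/(λz × AUC_INF), where Dose is the administered amount of the component analysed (imipenem or relebactam). AUC0-τ (τ = 6 h) will be reported as a descriptive exposure measure only. The percentage of AUC_INF extrapolated beyond the last sample will be listed for each participant.*

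Naming the component dose is a clarification, because the 1.25 g product combines three components. A sentence on how the points for λz are chosen would also help, since CL will now depend on it.

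The cost is two formulas and one listing. AUC_INF and λz are already planned outputs, so sampling, sample size and data capture do not change. In the simulated cases precision improves.

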2.1 Objectives

1. Determine the single-dose pharmacokinetics of intravenous imipenem (when administered as imipenem-cilastatin-relebactam 1.25 grams as a 30 minute infusion) in adult critically ill patients with known or suspected sepsis and ARC
2. Determine the single-dose pharmacokinetics of intravenous relebactam (when administered as imipenem-cilastatin-relebactam 1.25 grams as a 30 minute infusion) in adult critically ill patients with known or suspected sepsis and ARC
3. Determine a dose of imipenem-cilastatin-relebactam that achieves greater than 90% probability of pharmacodynamic target attainment using the imipenem *P. aeruginosa* susceptibility breakpoint of 2 µg/mL and the MIC distribution of a contemporary *P. aeruginosa* and KPC producing *K. pneumoniae* population
4. Assess the safety and tolerability of single-dose imipenem-cilastatin-relebactam in adult critically ill patients with known or suspected sepsis and ARC

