Study Day 2

- Clinical Assessments:
 - Perform a complete physical examination

	
 Record resting pulse, blood pressure, and respiratory rate; oxygen saturation (by pulse oximeter), including rate of supplemental oxygen (i.e., FiO₂); ventilator support; and highest (or lowest if hypothermia) daily temperature (oral, rectal, tympanic, or core) measured Identify, assess, and record any new adverse events or Serious Adverse Events (SAE) Laboratory Assessments: 
 Collect the following labs within 24 hours after completion of last blood sample collection: serum creatinine, blood urea nitrogen, glucose, sodium, potassium, chloride, bicarbonate, albumin, total protein, complete blood count (CBC) with differential, total bilirubin, direct bilirubin, alkaline phosphate, alanine aminotransferase, aspartame aminotransferase, and urine analysis with microscopy. 												
2.6 Study Duration	
 
 Final Protocol	2 months	
 
 IRB Approval	2 months	
 
 Enrollment and Sampling	10 months	
 
 Imipenem-relebactam Analytical (by Sponsor)	TBD	
 
 Pharmacokinetic Analyses	1 months	
 
 Final Report	1 months	
 
	Final Protocol	2 months	IRB Approval	2 months	Enrollment and Sampling	10 months	Imipenem-relebactam Analytical (by Sponsor)	TBD	Pharmacokinetic Analyses	1 months	Final Report	1 months
Final Protocol	2 months												
IRB Approval	2 months												
Enrollment and Sampling	10 months												
Imipenem-relebactam Analytical (by Sponsor)	TBD												
Pharmacokinetic Analyses	1 months												
Final Report	1 months												

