2.7 Statistical Analysis and Sample Size Justification	
Data Analyses
 
Data Collection Patient demographics, medical/surgical history, concomitant medications, and adverse event data will be collected throughout the study on a provided case report form. Protected Health Information (PHI) will be maintained at CAIRD.
 
Analysis Populations All patients enrolled will be included in the safety population. However, only the 8 patients who meet the definition of ARC will served as the primary pharmacokinetic population. Any additional patients enrolled who do not meet the definition of ARC will have imipenem and relebactam concentrations determined for informational purposes. These patients will not be included in the summary pharmacokinetic analyses.
 
Analytical Cryovials containing plasma and protein free filtrate will be overnight shipped on dry ice to Q2 Solutions (Ithaca, NY) for imipenem and relebactam concentration determination. The back-up vial will be shipped separately. Imipenem and relebactam concentrations will be determined by a liquid chromatography mass spectrometry assay.
 
Pharmacokinetic Analyses Non-compartmental Non-compartmental modeling will be conducted using WinNonlin (Pharsight Corporation, Cary, NC) using the latest version licensed for the laboratory. All concentration time curves will be plotted for visual inspection. The following pharmacokinetic parameters will be estimated for imipenem and relebactam in each of the 8 participants. The maximum concentration (C_{max}) will be the highest concentration observed for the concentration time profile of each participant. The time to maximum concentration (T_{max}) will be the observed sampling time of the C_{max}. The minimum concentration (C_{min}) will be the lowest concentration observed for the concentration time profile of each participant that occurs after the observed C_{max}. Lambda (λ_z) will be the resulting slope of the regression line
												

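### Objective 3 picks a dose by comparing a simulated target-attainment estimate with 90%, from a model of at most about 8 patients, and no statement of its uncertainty is planned

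*Combined protocol and SAP*

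**What the plan says.** - Section 2.1, Objective 3: "Determine a dose of imipenem-cilastatin-relebactam that achieves greater than 90% probability of pharmacodynamic target attainment", at the imipenem breakpoint of 2 µg/mL and for contemporary MIC distributions.
- Section 2.7, Population Pharmacokinetic Analyses: the concentrations "will be modeled using the non-parametric adaptive grid program (NPAG) with adaptive gamma", with one or two compartments. The text does not name the patients who enter this model.
- Section 2.7, Monte Carlo Simulation: "a 5000 patient Monte Carlo simulation will be conducted for the standard imipenem and relebactam dosing regimen". The thresholds are left to the sponsor's definition. If PTA is below 90%, "a higher dose and longer infusion time (e.g., 2-3 hours) will be simulated to determine a dose that achieves at least 90% PTA".
- Section 2.7, Analysis Populations: "only the 8 patients who meet the definition of ARC" form the primary pharmacokinetic population. Of any others enrolled: "These patients will not be included in the summary pharmacokinetic analyses". Section 2.3 likewise describes the pharmacokinetic analyses as being about patients with ARC.
- Section 2.7, Power/Sample Size: enrollment stops at 8 complete ARC patients "or a maximum of 12 patients complete the study, whichever occurs first". The sample size is justified for a 40% difference in clearance, and PTA is not mentioned.

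Neither section plans an interval for PTA, a way of carrying parameter uncertainty into the simulation, or a sensitivity analysis around 90%.

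**The concern.** The 90% cut-off does two jobs: it decides whether further regimens are simulated, and it decides when a dose has been found. Both decisions use a point estimate. A simulation of 5000 looks precise, but every simulated patient is drawn from a model fitted to at most 8 real ones. There could be fewer than 8, because enrollment also stops at 12 completers whether or not 8 of them have ARC. Extra draws cannot reduce the error in that fitted model.

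Followed as written, the plan can report a regimen as reaching 90% when it does not, or send the search onward when the regimen already did. The reader of the results would have nothing to show how uncertain the answer is.

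**Working it through.** **Step 1. The plan's own figure.** Inputs from Section 2.7, Power/Sample Size: mean clearance 8.6 L/h, 40% difference, CV 25%, n = 8, alpha 0.05, stated power 80%. The sidedness and the base for the CV are not stated. I take a two-sided one-sample t-test against the historical mean, with the CV applied to the shifted mean.
- Difference: 0.40 × 8.6 = 3.44 L/h.
- SD: 0.25 × (8.6 × 1.4) = 0.25 × 12.04 = 3.01 L/h.
- Noncentrality: (3.44 / 3.01) × √8 = 3.23. Critical t on 7 df: 2.365.
- Power: 79.1%, which agrees with 80%.

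The sample-size statement reproduces. It concerns clearance and gives no information on the precision of PTA.

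**Step 2. What 5000 draws achieve.** At PTA 90%, the 95% half-width from simulation alone is 1.96 × √(0.9 × 0.1 / 5000) = 0.0083, or about ±0.8 points.

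**Step 3. What 8 patients leave open (illustration).** The sponsor's target is not given, so the trial's own PTA cannot be computed. Assume instead that attainment depends on one log-normal exposure, measured without error, with mean and SD estimated from n = 8. Then PTA = Φ((μ − c)/σ), where c is the threshold on the log scale. √n times the standardized estimate follows a noncentral t with n − 1 = 7 df and noncentrality √n × z(true PTA). The CV cancels.

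*Interval at an estimated PTA of 90%.* z(0.90) = 1.2816, and 1.2816 × √8 = 3.625. Find the noncentralities that put 3.625 at the 97.5th and 2.5th percentiles:
- Lower: 0.859, divided by √8 = 0.304, so Φ = 61.9%.
- Upper: 6.263, divided by √8 = 2.214, so Φ = 98.7%.

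*Chance that a fixed regimen passes the 90% rule.* This is P(noncentral t ≥ 3.625):

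| True PTA | Noncentrality | Passes |
|---|---|---|
| 70% | 1.483 | 6.9% |
| 80% | 2.380 | 21.1% |
| 85% | 2.931 | 34.6% |
| 90% | 3.625 | 54.3% |
| 95% | 4.652 | 80.0% (fails 20.0%) |
| 99% | 6.580 | 98.5% |

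**Step 4. What a simple count would show.** The exact (Clopper-Pearson) 95% interval for 8 of 8 patients attaining has lower limit 0.025^(1/8) = 0.631, so 63% to 100%. For 7 of 8 it is 47.3% to 99.7%.

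**Step 5. How a bootstrap would behave.** A resample of 8 holds on average 8 × (1 − (7/8)^8) = 5.25 distinct patients. In the same simplified model (5,000 simulated studies, 1,000 resamples each), a nominal 95% percentile bootstrap covered the true PTA in 81.6%, 79.8% and 78.6% of studies at true PTAs of 80%, 90% and 95%. Such an interval is too narrow at this n.

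**The case against.** The strongest reply has four parts.

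- **The numbers are not this trial's.** The real model is non-parametric, for two drugs, with covariates, and the target is undisclosed. The pass rates are for one fixed regimen, whereas the plan searches over regimens. This stands: the figures show the order of magnitude and are not the plan's operating characteristics. Real intervals could be wider or narrower.
- **Regimens well under 90% seldom pass.** A reader might infer that a clearly inadequate regimen could readily be declared adequate. The illustration does not support that: a true PTA of 70% passes in about 7% of studies. Nor do the documents show that any candidate regimen lies near the cut-off. This narrows the concern.
- **The remedy is imprecise.** A bootstrap covering about 80% instead of 95% should not be the required core of the fix, and the count is coarse. This stands for the bootstrap, which should be optional. The count's coarseness reflects how little 8 patients can say, and that is worth showing.
- **It is a small observational pharmacokinetic study.** The simulation alters no participant's treatment. True, but Objective 3 is a stated objective with a numerical criterion and is not labelled exploratory. A small sample is a reason to show uncertainty.

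A reader might also infer that up to 12 patients feed the model, because the population-model text names no population. Sections 2.3 and 2.7 (Analysis Populations) point the other way, to ARC patients only. One clarifying sentence would settle it.

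**Conclusion.** The concern holds in a limited form. Objective 3 is settled by a point estimate against 90%, from a model of at most 8 ARC patients on the natural reading, with no uncertainty statement planned for PTA. That part rests on the documents alone.

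The size rests on the single-exposure, log-normal, error-free assumption with n = 8. On that basis an estimate of 90% leaves a true PTA anywhere from about 62% to 99%, and misclassification matters mainly for true PTAs of about 80% to 95%. Regimens far from the cut-off are little affected.

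It would be wrong to conclude that the sample-size calculation is in error, since it reproduces for its own purpose, or that any particular regimen will be misjudged. The plan should be changed before analysis, but this does not threaten the pharmacokinetic objectives.

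**What to change.** In Section 2.7:

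1. Report each simulated PTA with a statement of the uncertainty from estimating the model in so few patients. At minimum, at the 2 µg/mL breakpoint, give the number of modelled ARC patients who attain the target on their own fitted parameters, with the exact 95% interval. Note that this is coarse, treats each patient's attainment as known, and cannot separate regimens that all patients attain. A patient bootstrap with refitting is optional. If used, label it approximate and likely too narrow, and report the number of failed refits.
2. Word the Objective 3 conclusion as an estimated PTA with its uncertainty, and do not describe 90% attainment as established on the point estimate alone.
3. State in one sentence that the population model uses ARC patients only.
4. Reconcile the strict inequality in Section 2.1 with the non-strict one in Section 2.7. This is wording only.

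Cost: a few lines of text and minor analysis work. The optional bootstrap would add repeated refits for each drug within the 1 month that Section 2.6 allots to pharmacokinetic analyses. The headline becomes less definite. No extra patients are needed and no dose changes.
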